The study aims to assess whether an FDA-approved rapid turnaround test (RTAT) for *Neisseria gonorrhoeae* and *Chlamydia trachomatis* infections will lead to more appropriate antibiotic prescription in the emergency department.

Secondary outcomes include the RTAT's effect on length of emergency department stay, result congruence with the PCR method regardless of specimen source, result congruence with PCR method differentiating between urine and cervical specimens, estimation of the effect of utilization of the RTAT will have on healthcare costs, its impact on satisfaction, and on further healthcare utilization.

Null hypothesis: Point of care use of the GC/CT RTAT in female ED patients for whom there is a suspicion of either disease results in no more appropriate antibiotic prescription than in patients who receive empiric therapy before GC/CT PCR results return.

B. Background Significance

Infections with *Chlamydia trachomatis* and *Neisseria gonorrhoeae* are the most commonly reported sexually transmitted diseases in the United States. In 2014, there were 1,441,789 cases of chlamydia and 350,062 cases of gonorrhea reported in the US (CDC, 2014). Baltimore ranks 4th in US metropolitan areas for rates of chlamydia at 1245 cases per 100,000 and 17th for rates of gonorrhea at 314 cases per 100,000 (CDC, 2014).

Untreated infections leave patients at increased risk of pelvic inflammatory disease, infertility, ectopic pregnancy and shedding of the human immunodeficiency virus among other morbidities (Johnson and Mak, 2002). Because of this, providers have a low threshold to initiate treatment for gonorrhea and chlamydia. In a previous retrospective analysis done at this hospital and a nearby community hospital it was found that patients were inappropriately treated 21% of the time (Holley et al., 2015). Inappropriate treatment is defined for the purpose of this study as administration of antibiotics to treat GC/CT in the absence of GC/CT infection or failure to give antibiotics in the presence of GC/CT infection. For the purposes of the study the "gold standard" result will be that of the PCR test and not the RTAT. By evaluating the impact of a rapid turnaround test for GC/CT, we will determine if there is a reduction in the rate of inappropriate treatment. Furthermore, we will analyze the economic, temporal, and qualitative impacts of altering the current paradigm.

C. Research Design

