A prospective, nonblinded, randomized controlled trial will be conducted at the Adult Emergency Department at the University of Maryland Medical Center and Adult Urgent Care Center, which is managed by the Department of Emergency Medicine, located in Baltimore, Maryland.

Sample size calculation was performed assuming that the control group will be given the wrong treatment 21% of the time. It is assumed that the use of the rapid TAT will reduce this by about 95%. The following variables were used to calculate the sample size: alpha = 0.05 power = 0.8 P0 = 0.21 P1 = 0 M = 1. It was determined that 43 patients are required in each group.

Assuming a dropout rate of up to 10% this study will enroll 48 patients into each of the study groups.

Patients who consent to participation will be randomly selected into either the control group or the experimental group.

- i. Control group - GC/CT testing done only via standard PCR test
- ii. Experimental group - GC/CT testing done using both rapid TAT and standard PCR tests

Subjects will be randomly assigned to either the study or control groups. Randomization will be performed at the level of the patient, with the study team member using blind-sequenced subject folders. Patients will be assigned a sequential subject number with a corresponding folder for the study team member. This folder will contain the randomly assigned treatment allocation and data collection forms. Randomization for the subject folders will be performed using an online randomization tool.

Study team members will assess patients for inclusion and exclusion criteria. Patients who meet criteria will be invited to participate in the study.

Informed Consent Process: Patients who meet study criteria and desire to be a part of this study, will be consented prior to procedure. A copy of the consent and research proposal will be provided and reviewed with the patient. This study will be voluntary and confidential. All patient identification information will be kept in the principal investigator's locked office.

Study Location: Study will be conducted in the Adult Urgent Care Center and Emergency Department at the University of Maryland Medical Center.

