All study participants that will be enrolled will undergo standard of care testing to evaluate for a sexually transmitted infection. If the result of the RTAT in the experimental group is "invalid" treatment will still be at the discretion of the provider using the information available including history, physical and determination of risk. No repeat testing with the RTAT is allowable as part of study procedures.

During the subject screening and consent process, we hope to identify subjects that are not willing to wait for the results of their testing should they be a part of the experimental group and not enroll them in the study. Should these subjects enroll in the study and subsequently change their mind about waiting for their results, they may choose to withdraw from the study and leave. If the RTAT sample is already being run on the machine at the time of the subject's departure, the subject will be contacted with the test result. If the test result is positive they will be counseled about appropriate next steps taking into account whether or not they received empiric treatment. All study participants that will be enrolled will undergo standard of care testing to evaluate for a STI. Per usual care at the University of Maryland Medical System, the clinical provider determines treatment at the time of initial evaluation using all the available clinical information. For patients assigned to the intervention group- If the subject leaves prior to completion of the RTAT then the clinical provider still determines treatment based on the information available.

In a study published by Gaydos et al in 2013, the Cepheid RTAT for chlamydia in females demonstrated sensitivities for endocervical, vaginal, and urine samples of 97.4%, 98.7%, and 97.6%, respectively, whereas, for gonorrhea in females the sensitivities for endocervical, vaginal, and urine samples were 100.0%, 100.0%, and 95.6%, respectively. [doi: 10.1128/JCM.03461-12]. This demonstrates a very high accuracy for the test under consideration in the current study. There is always the possibility of incongruent results between

the standard of care PCR test and the Cepheid RTAT. If this happens the study subject will be contacted and arrangements will be made to have the appropriate care provided.

The possible outcomes for test results are:

1. RTAT is negative and PCR is negative: no adjustment needs to be made to care of the subject.

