2. RTAT is negative and the PCR is positive: if the patient was not treated empirically during the index visit, as usual care for the department, the patient will be contacted and arrangements made to provide appropriate care. This contact is made as part of the quality assurance program of the department. The study team will verify this contact was completed.
3. RTAT is positive and PCR is positive: no adjustment needed if the clinician treated the patient during the index visit. If the patient was not treated then the same process will occur as in scenario 2.
4. RTAT is positive and PCR is negative: if the subject was not treated during the index visit then they will be contacted by the study team to explain that two highly accurate tests gave different results. The patient will be offered the opportunity to return for treatment. If the subject was treated during the index visit then they will be contacted by the study team to explain that two highly accurate tests gave different results. As treatment was already given there would be no change to the management of the patient.

D. Subjects and Sampling

a. Inclusion Criteria

- Female patients age 18-55
- Signs or symptoms consistent with sexually transmitted infection
- Medical provider willing to consider the result of the rapid turnaround test in the decision to treat for gonorrhea/chlamydia
- Must have a urine specimen obtained and a pelvic exam performed as part of the anticipated standard of care evaluation
- Patient agrees to wait for results of RTAT testing, in the likelihood they are assigned that group.
- Provides informed consent

b. Exclusion Criteria

- Age < 18 or > 55
- Signs of systemic infection
- Patient in whom the provider is unwilling to consider the result of the rapid turnaround test
- Patient who reports being treated for either gonorrhea or chlamydia in the preceding 3 months
- Patients undergoing evaluation for sexual assault
- Patients that are known to be pregnant or express concern that they may be pregnant
- Incarcerated patients
- Students/Employees of the facility
- Presence of any other condition(s) that the investigator feels makes the patient unsuitable for study inclusion.

c. Informed Consent Process: Patients who meet study criteria will be consented prior to participation in any study related procedure. A copy of the consent form and privacy form

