(HIPAA) will be provided and reviewed with the patient. This study will be voluntary and confidential. All study data with potential patient identifiable information will be kept in a locked office.

- d. Study Location: Study will be conducted in the Adult Urgent Care Center at the University of Maryland Medical Center, which is managed by the Department of Emergency Medicine and in the Adult Emergency Department.
- e. Potential Problems: Insufficient number of patients who meet all inclusion and exclusion criteria. Lack of eligible patients willing to participate in the study.

E. Data Collection and Objectives

Primary Outcomes:

- To evaluate the effect of utilizing a rapid turnaround GC/CT test on treatment of patients with possible STIs

Secondary Outcomes:

- To evaluate the effect of utilizing a rapid turnaround GC/CT test on length of stay in the Emergency Department
- To compare the congruence of test results between the rapid turnaround GC/CT test with the usual care test (send out PCR) in those subjects that have both performed (Experimental Group).
- To evaluate the effect of utilizing a rapid PCR test on healthcare costs.
- To evaluate patient satisfaction with the 2 diagnostic groups.
- To compare need for additional healthcare utilization between the groups.

F. Methods

Patients meeting eligibility criteria and who have signed the research informed consent will be enrolled in this study. The subject will be randomly assigned to either the control or the experimental group. We will utilize the online pre-randomization website:

<https://www.graphpad.com/quickcalcs/randomize1.cfm> for randomization into one of the two groups. All subjects will be assigned a study participant number. Subject data collected will include demographic information, symptoms of the present illness and physical exam findings.

The control group will be followed according to standard of care as listed below in Question 2. The medical records will be reviewed following treatment and discharge to determine if this subject received empiric treatment.

The experimental group will be followed according to standard of care with the following additional research analysis: A cervical swab sample will be analyzed with the RTAT. The RTAT has been approved by the FDA for diagnosing suspected sexually transmitted infections (STIs).

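### The sample size calculation uses P1 = 0, a 100% reduction in wrong treatment, although the text assumes about 95% (P1 = 0.0105); 43 per group follows from the zero

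*Protocol*

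**What the plan says.** Section C of the Protocol (Research Design) takes a control wrong-treatment rate of 21% and states the expected effect: "It is assumed that the use of the rapid TAT will reduce this by about 95" per cent. It then lists the variables used, "alpha = 0.05 power = 0.8 P0 = 0.21 P1 = 0 M = 1", and concludes: "It was determined that 43 patients are required in each group". Allowing for 10% dropout, it enrols 48 per group.

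Other parts of the Protocol bear on whether the experimental rate can be zero:

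- Section B counts both treatment without infection and non-treatment of infection as inappropriate. It says that the reference "result will be that of the PCR test and not the RTAT".
- Section C cites a published evaluation in which the rapid test for chlamydia in women "demonstrated sensitivities for endocervical, vaginal, and urine samples of 97.4%, 98.7%, and 97.6%, respectively". Section F says "A cervical swab sample will be analyzed with the RTAT", so the 97.4% endocervical figure is the relevant one. The Review of Literature gives a specificity of 99.4% to 99.9%.
- Section C lists the four combinations of rapid test and PCR results. For a patient who is rapid-test positive, PCR negative and already treated, it says "As treatment was already given there would be no change to the management of the patient".
- For an invalid rapid test, section C leaves treatment to the provider and adds "No repeat testing with the RTAT is allowable as part of study procedures". Section F allows treatment after a negative rapid test.

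**The concern.** The stated effect and the listed input are next to each other and disagree. A 95% reduction leaves about 1 wrong treatment in 100 patients; P1 = 0 leaves none. The difference is small in absolute terms, but sample size formulas are sensitive to it when one rate is near zero.

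Zero is also a value that the Protocol's own rules do not allow for. A treated patient with a positive rapid test and a negative PCR is inappropriately treated under section B, and section C plans for that patient. A missed infection, an invalid result, or treatment despite a negative result can each produce a wrong treatment as well.

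At stake is whether the 80% power claimed for 43 per group applies to the effect that the text describes, or only to a rapid-test arm free of error.

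**Working it through.** **Inputs (Protocol, section C).** P0 = 0.21, alpha = 0.05, power = 0.80, 1:1 allocation, listed P1 = 0. The stated reduction gives P1 = 0.21 × (1 − 0.95) = 0.0105. Two-sided testing is my assumption; the normal quantiles are 1.960 and 0.842.

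**Formula.** Let Δ = P0 − P1 and p̄ = (P0 + P1)/2. With the average-proportion variance under both hypotheses,

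n = (1.960 + 0.842)² × 2 p̄(1 − p̄) / Δ²

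and with continuity correction,

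n_c = (n/4) × [1 + √(1 + 4/(nΔ))]².

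**Reproducing the plan's figure, P1 = 0.** Δ = 0.21 and p̄ = 0.105. Then n = 7.849 × 2 × 0.105 × 0.895 / 0.0441 = 33.45, and n_c = 42.44, rounded up to **43**. For dropout, 43/0.90 = 47.8, rounded up to **48**. Both stated figures are reproduced from the printed inputs.

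**Same formula at the stated effect, P1 = 0.0105.** Δ = 0.1995 and p̄ = 0.11025. Then n = 7.849 × 2 × 0.11025 × 0.88975 / 0.0398 = 38.69, and n_c = 48.19, rounded up to **49**.

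**Power by that formula at P1 = 0.0105.** Inverting the correction gives an effective size n' = (nΔ − 1)²/(nΔ²), and power = Φ(Δ√(n'/(2p̄(1 − p̄))) − 1.960).

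- 43 per group: n' = 33.56, Φ(2.609 − 1.960) = 74.2%.
- 48 per group: n' = 38.50, Φ(2.795 − 1.960) = 79.8%.

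A close variant, with separate variances under the alternative and the same correction, gives 42 at P1 = 0 and 47 at P1 = 0.0105. Its power at 0.0105 is 75.3% at 43 and 81.1% at 48.

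**Exact power (enumeration of both binomials, two-sided 0.05).**

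| Test | P1 = 0, n = 43 | P1 = 0.0105, n = 43 | P1 = 0.0105, n = 48 |
|---|---|---|---|
| Fisher | 91.3% | 82.4% | 87.6% |
| Chi-square, continuity-corrected | 91.3% | 81.5% | 87.6% |
| Chi-square, uncorrected | 98.8% | 94.2% | 96.3% |

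**Can P1 be zero?** Take chlamydia alone, with every provider following the rapid test. The wrong-treatment rate from test error is q × (1 − 0.974) + (1 − q) × (1 − specificity), where q is the prevalence of infection among enrolled patients. The Protocol does not give q, so I assume 5% to 20%.

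- q = 5%, specificity 99.9%: 0.0013 + 0.00095 = 0.23%.
- q = 20%, specificity 99.4%: 0.0052 + 0.0048 = 1.00%.

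The range is above 0 and within the 1.05% that the text implies. The cited accuracy figures need not have used this trial's PCR as their reference, so this is only an indication.

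**The case against.** The case for leaving the paragraph alone has several parts.

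*Zero may be 0.0105 rounded.* At the two decimals used for P0, 0.0105 rounds to 0.01, not 0. The rounding would also matter, because the formula that gives 43 at zero gives 49 at 0.0105.

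*The arithmetic is sound.* This stands. A reader who tries only the uncorrected formula or Fisher's test at P1 = 0 (37 per group at 80% power) might infer that 43 is a calculation error. It is not, since the printed inputs give 43 by a standard formula. Exact continuity-corrected chi-square at P1 = 0.0105 also first reaches 80% at 43 (79.9% at 42, 81.5% at 43). The agreement at P1 = 0 is therefore not proof of how 43 was obtained, but zero is the input that the Protocol lists.

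*No power is lost.* This stands in part. All three exact tests keep more than 80% at the stated effect with 43 per group. A reader might infer from the 49 that the trial is underpowered, or must enrol 49/0.90 = 54.4, so 55 per group. The document does not support that: the shortfall appears only in the continuity-corrected approximations, and the primary test may be set in an analysis plan that is not shown.

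*Eligibility limits the routes to wrong treatment.* Section D requires a provider willing to consider the rapid test and a patient who agrees to wait. These criteria reduce the routes but do not close them. A reader might go further and infer an experimental rate of several per cent, with power well below target. The Protocol gives no figure for treatment against the rapid test or for invalid results, and the test-error range above fits the stated 95%, so that inference is unsupported.

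**Conclusion.** The concern holds as a contradiction between the stated effect and the input used. Section C assumes about 95% but calculates with 100%, and the zero cannot be squared with the Protocol's own reference standard, discordant-result plan, cited accuracy and provider discretion.

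By the formula that reproduces 43, the difference is 43 against 49 per group. Power at the stated effect is then about 74% with 43 evaluable and 80% (79.8%) with 48. By exact calculation the target is met, with 82% and 88% for Fisher and 94% and 96% for uncorrected chi-square. Whether 80% power holds at the stated effect thus depends on the test, and a failure to reach it is not shown.

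This rests on P0 = 0.21, a reduction of exactly 95% and two-sided testing at 0.05. The contradiction itself needs none of the power calculations.

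**What to change.** In the sample size paragraph of section C, replace P1 = 0 with P1 = 0.0105, so that the input agrees with the stated 95% reduction. Restate the power at that value for 43 evaluable and 48 enrolled per group, under the test that will be used: for example, 82% and 88% for Fisher's exact test, or about 74% and 80% by the continuity-corrected formula that reproduces 43.

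The cost is one corrected paragraph. Enrolment and conduct need not change. The downside is a stated power less favourable than P1 = 0 suggests; if the continuity-corrected formula is kept as the basis, the paragraph would have to say that 43 evaluable patients per group fall short of 80% at the stated effect.

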For the experimental group, a study team member will verbally obtain the consent of the treating provider for the subject as to whether or not they would empirically treat the study subject if the RTAT was not being run. After results of the RTAT test are obtained the treating provider will be given the results. The treating provider can determine the course of treatment based on this test and their history of clinical exam findings. Subjects with negative RTAT results are not precluded from receiving treatment. If the result of the RTAT of the experimental group is

“invalid”, the subject will be treated according to usual care and, at the discretion of the provider. This may be to either empirically treat or wait to treat pending the results of the usual care tests. This process to either treat or withhold antibiotics for a suspected sexually transmitted infection (STI) until the culture results have returned is in accordance with the standard of care for the University of Maryland Medical System.

For both groups- 1) Additional data will be collected on length of stay in the Adult Emergency Department and Urgent Care Center. The time of interest is from when the subject first undergoes pelvic examination to the time that the subject leaves the treatment area.

2) A patient satisfaction survey to compare assigned treatment groups. 3) Telephone contact 1 to 2 weeks after enrollment. Using a standardized interview form they will be asked about resolution of symptoms, need for additional treatment, compliance with treatment, and satisfaction.

Subjects who have enrolled in the study and subsequently changed their mind about waiting for their results may choose to leave. All study participants who will be enrolled will undergo standard of care testing to evaluate for a STI. Per standard of care at the University of Maryland Medical System, they will be treated empirically or have antibiotics withheld at the discretion of the provider until the culture results have returned, after the subject has been discharged.

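### Does asking the provider about intended treatment in the experimental group only spoil the comparison between the groups?

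*Protocol*

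**What the plan says.** In F. Methods the Protocol states: "For the experimental group, a study team member will verbally obtain the consent of the treating provider". What is asked is put this way: "as to whether or not they would empirically treat the study subject if the RTAT was not being run". The word consent reads oddly, but the content is a question about intended treatment. The text then continues: "After results of the RTAT test are obtained the treating provider will be given the results". The provider then decides freely on the test result and the clinical findings, and a negative result does not rule out treatment.

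For controls the same section says "The control group will be followed according to standard of care as listed below in Question 2" and, on how their treatment is captured, "The medical records will be reviewed following treatment and discharge to determine if this subject received empiric treatment". The shared procedures begin "For both groups- 1) Additional data will be collected on length of stay" and go on to a satisfaction survey and a telephone contact. None of them is a question to the provider. F. Methods introduces the experimental group as standard care with the rapid test (RTAT) added, and only afterwards describes the question.

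The outcome is defined in B. Background Significance: "Inappropriate treatment is defined for the purpose of this study as administration of antibiotics to treat GC/CT in the absence of GC/CT infection". Leaving an infected patient untreated counts as well, with PCR as the reference. The trial is declared nonblinded in C. Research Design. The inclusion criteria already require, for every patient, a provider willing to consider the rapid-test result.

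**The concern.** The endpoint is a decision by the treating provider. In one group that provider is asked to state the decision to study staff before the result arrives; in the other group nobody asks. Committing to an answer can make a clinician reflect, or hold to what was said. A difference between the groups could then contain an effect of being asked as well as an effect of the test.

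There is a second worry. The answer is given in the knowledge that a result is coming. No control has both a stated intention and an actual decision, so how well intention predicts treatment without the rapid test cannot be checked patient by patient, and it cannot be recovered later.

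With 43 per group and almost no errors expected in the experimental group, a few changed decisions could matter.

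**Working it through.** **1. The two groups side by side.**

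| Element | Experimental | Control |
|---|---|---|
| Provider willing to consider the rapid test (eligibility) | yes | yes |
| Question on intended treatment without the rapid test | yes | not described |
| Rapid-test result given to provider | yes, after the question | no |
| Actual treatment known | yes | yes, from record review |

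The asymmetry is real. The question asks what the provider would do without the rapid test. For a control that condition holds in fact, so the decision made is the counterpart of the answer. What is missing is only an intention-and-action pair within the same control.

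**2. Who uses the answer?** The aims and the outcome list cover treatment, length of stay, agreement with PCR, cost, satisfaction and further healthcare use. None uses the stated intention. A description within the experimental group (would have treated against did treat) needs no control pair.

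**3. The plan's own sample size.** The inputs in C. Research Design are "alpha = 0.05 power = 0.8 P0 = 0.21 P1 = 0 M = 1". With p1 = 0.21, p2 = 0, mean 0.105, d = 0.21 and a two-sided test:

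n = [1.96·√(2·0.105·0.895) + 0.8416·√(0.21·0.79)]² / 0.21² = 32.2

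With continuity correction: (32.2/4)·[1 + √(1 + 4/(32.2·0.21))]² = 41.2, so 42 against the stated 43. Then 43/0.9 = 47.8, which gives the stated 48. The provider question enters none of these inputs.

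**4. What a prompt effect could do (assumptions only).** The documents give no size or direction. Take one extra error in 43 in the experimental group (1/43 = 0.0233). Exact binomial enumeration, 43 per group, control error 0.21, two-sided 0.05:

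| Experimental error | Chi-square power | Fisher power |
|---|---|---|
| 0 (the plan's P1) | 98.8% | 91.3% |
| 0 + 1/43 = 0.0233 | 86.0% | 71.9% |
| 0.21 × 0.05 = 0.0105 (the 95% reduction in words) | 94.2% | 82.4% |
| 0.0105 + 1/43 = 0.0338 | 78.0% | 63.2% |

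Single tables: 9/43 against 0/43 gives chi-square p = 0.0015 (Fisher 0.0025); 9/43 against 1/43 gives p = 0.0071 (Fisher 0.0148). Both are significant.

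In the flattering direction, suppose the rapid test did nothing and the question alone cut the 21% error by 2, 5 or 10 points. A significant benefit would then appear in about 4%, 9% or 24% of trials, against 2.5% with no prompt effect (normal approximation). At the plan's P1 = 0 the question cannot lower the error further.

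**5. What asking controls as well could cost (same kind of assumption).** If prompted controls made one error fewer in 43, control error would be 0.21 − 0.0233 = 0.1867. Power would be 97.1% (Fisher 83.9%) at P1 = 0 and 89.9% (Fisher 72.5%) at 0.0105. One error more (0.2333) gives chi-square power of 99.5% and 96.8%. So the remedy carries a possible loss of the same kind as the harm it is meant to prevent.

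**The case for a change.** The strongest case for acting is that the question bears directly on the primary-endpoint decision, in an open trial, in one group only. The opening description of the experimental group leaves it out. A result does not always follow either: the rapid test may be invalid, or the patient may leave before it finishes, and the provider then decides with nothing to dilute the earlier answer. Asking everyone before the folder is opened would mean about 96 questions instead of 48, at a point where the provider has to be approached anyway.

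The asymmetry stands, and so does the point about invalid or unfinished tests, although the Protocol gives no frequency for them. The rest carries less weight. The question is not hidden; it is set out in F. Methods, and only a label calling it part of the strategy is absent.

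Extending it to controls is not neutral. It would prompt providers who receive no rapid-test result afterwards, and so move the comparator away from the standard care that the Protocol specifies. If asked before allocation, it may also come before the pelvic findings and be less informative. The milder remedy, a sentence declaring the question part of the strategy, is harmless but alters no data, analysis or result.

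**Conclusion.** The observation is correct, but no change to the plan follows. The groups differ by the rapid test and by one openly described question. The effect of that question is unknown and probably small, because the rapid-test result normally reaches the provider afterwards and providers in both groups were already selected for willingness to consider that result.

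The controls' actual treatment provides a group-level counterpart to the answer, and no stated objective needs a patient-level one. Keeping controls unprompted is a fair trade-off, and an analyst would naturally treat the answer as description within the experimental group.

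The power figures rest on an assumed shift of one decision in 43. They show sensitivity at this sample size and are not evidence of bias. The stated 43 and 48 per group are untouched.
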